## **4.1 OVERVIEW OF STUDY DESIGN/INTERVENTION**

### **4.2 Design**

This is a single institution study involving patients with synovial sarcoma who have completed all standard therapy (e.g. surgery +/- radiation to the primary site) +/- any adjuvant chemotherapy. The sequence and types of therapy offered prior to WLI will likely vary based on primary tumor site, tumor resectability, extent of metastatic disease, performance status, and comorbidity. Each patient's therapy will be determined by the disease management team irrespective of participation on this protocol.

Patients are eligible for this protocol if their pulmonary metastases are present at diagnosis or develop over the course of treatment. After completion of all planned therapy, patients will be assessed with a CT scan of their lungs and a PET scan if the CT scan shows residual lung metastases. Assuming there is no residual pulmonary disease or that any remaining pulmonary metastases are  $\leq 2$  cm, patients will proceed to WLI. If there is gross disease in the lung  $>2$  cm, patients will be evaluated for metastasectomy. If they undergo metastasectomy and subsequently have no residual pulmonary disease or have pulmonary metastases  $\leq 2$  cm, they are eligible to receive WLI on this protocol. Patients will also have an echocardiogram and pulmonary function tests (PFTs) prior to initiation of whole lung irradiation to assess baseline cardiac and pulmonary function. Patients will be simulated for external beam radiation with the use of a 4D CT to account for respiratory motion, as per standard practice. Patients will be treated with IMRT to 1500cGy in 150cGy fractions.

After completion of WLI, patients will be followed by members of the Radiation Oncology department for toxicity evaluations and will be evaluated by physical exams and chest CT scans at 3, 6, 12, 18, and 24 months (+/-3-6 weeks depending on timepoint). Patients will also have echocardiograms at 6 months (+/- 3 weeks) and 12, and 24 months (+/- 6 weeks). Patients will also undergo pulmonary function tests (PFTs) at 6 months (+/- 3 weeks) and 24 months (+/- 6 weeks). Any severe toxicity due to radiation will be carefully evaluated and further accrual will be terminated if the level of toxicity is greater than expected. The protocol may be terminated or modified as determined by the principal investigator. Please see section 11.0 regarding specific dose limiting toxicities and stopping rules for the protocol.

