### **6.1 CRITERIA FOR SUBJECT ELIGIBILITY**

## 6.2 Subject Inclusion Criteria

- Patients with synovial sarcoma confirmed by MSKCC pathological review
- Patients with single or multiple lung metastases at diagnosis or that develop over the course of treatment.
- After completion of all chemotherapy, lung metastases must be  $\leq 2$  cm.
- Age  $\geq 12$  months of age
- Karnofsky performance status (KPS) must be  $\geq 70$  for patients  $\geq 16$  years of age and Lansky performance status must be  $\geq 70$  for patients  $< 16$  years of age.
- Normal cardiac function
  - No active coronary artery disease;
  - No New York Heart Association class II, III or IV disease;
  - No arrhythmia requiring treatment.
  - Baseline echocardiogram with a shortening fraction of  $\geq 27\%$  or an ejection fraction  $\geq 50\%$ .
- Female patients of childbearing potential must have a negative pregnancy test within 14 days of radiation start.
- Female patients who are lactating must agree to stop breast-feeding.
- Sexually active patients of childbearing potential must agree to use effective contraception.

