### **12.2 Assessment of Secondary Objectives**

### **12.2.1 Assessment of Pulmonary Failure-Free Survival**

A CT scan of the chest will be obtained at 3 and 6 months (+/- 3 weeks) and at 12, 18, and 24 months (+/- 6 weeks) post-treatment. This study will use a modified Response Evaluation Criteria in Solid Tumor (RECIST) for assessment of tumor response. The baseline scan will be the pre-irradiation CT scan.

All patients will be assessed as failure or failure free as defined below. Pulmonary failure-free survival will be defined as survival with no progressive disease in the lungs. CR, PR, and SD will be considered failure-free.

For patients with measurable ( $\geq 5\text{mm}$  but  $<10\text{mm}$ ) lung lesions at the time of study entry:

- a. The investigator will identify up to 5 measurable lung lesions to be followed for response. The sum of the longest diameter (LD) for all target lesions will be calculated and reported as the disease measurement.
- b. Complete response (CR) is defined as the disappearance of all target lesions.
- c. Partial response (PR) is defined as at least a 30% decrease in the disease measurement, taking as reference the pre-irradiation CT scan.
- d. Progressive disease (PD) is defined as at least a 20% increase in the disease measurement, taking as reference the smallest disease measurement recorded since start of treatment, or the appearance of one or more new lung lesions.
- e. Stable disease (SD) is neither sufficient shrinkage to qualify for PR nor sufficient increase to qualify for PD.

For patients with no measurable disease present at baseline:

- a. Stable disease (SD) is defined as no appearance of measurable lesions in the treated area
- b. Progressive disease (PD) is defined as the appearance of measurable lesions on post-treatment scans and will be considered failure-free if no measurable lesions develop.

**12.2.2 Assessment of overall survival** will be performed for each patient using clinical data and information from the social security database.

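### For patients whose lung nodules are all under 5 mm at entry, the 5 mm line that classifies them also defines failure, so a trivial reading change scores as pulmonary failure

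*Combined protocol and SAP*

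**What the plan says.** **Who can enter.** Section 6.2 gives only an upper limit: "After completion of all chemotherapy, lung metastases must be" no larger than 2 cm. Section 4.2 also admits patients with nothing left in the lung ("Assuming there is no residual pulmonary disease or that any remaining pulmonary metastases are" within 2 cm). Neither sets a lower size limit, so a patient whose remaining nodules are all under 5 mm is eligible.

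**How they are classified.** The only definition of measurable in Section 12.2.1 is at least 5 mm but below 10 mm, applied to "lung lesions at the time of study entry". Everyone else comes under the clause that begins "For patients with no measurable disease present at baseline". That clause covers both patients with no nodules and patients with visible nodules below 5 mm.

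**How failure is scored in that group.** Item (a): "Stable disease (SD) is defined as no appearance of measurable lesions in the treated area". Item (b): "Progressive disease (PD) is defined as the appearance of measurable lesions on post-treatment scans". Neither item mentions percentage growth, absolute growth, the nodule's earlier size or a confirmatory scan.

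**The other group.** Item (d) for measurable disease reads "Progressive disease (PD) is defined as at least a 20% increase in the disease measurement", taken against the smallest measurement since the start of treatment, or the appearance of a new lung lesion.

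**Where it feeds in.** "Pulmonary failure-free survival will be defined as survival with no progressive disease in the lungs". Section 14.0 estimates this endpoint by cumulative incidence, with other progression and death as competing risks. Chest CT is scheduled at 3, 6, 12, 18 and 24 months.

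**The concern.** A failure rule should register change. Here it registers which side of a fixed line a reading falls on, and it is the same line used to sort patients at entry. A nodule just below 5 mm can cross it through reading error alone. There are five scheduled chances to cross, and one crossing is permanent in a cumulative incidence analysis.

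Pulmonary failure-free survival is the trial's only lung-control endpoint, and there is no control arm in which the same artefact would also appear. One false failure among 15 patients moves the crude proportion by 1/15 = 6.7 percentage points. The shift is larger if fewer patients are evaluable, since Section 13.0 restricts this endpoint to patients who complete radiation and have at least one follow-up CT.

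A minimum-growth rule added to item (d) would not help, because item (d) does not apply to these patients.

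**Working it through.** The plan states no power, error rate or target for this endpoint, so there is no figure to reproduce. The check is of the rule's logic, then of its behaviour under stated assumptions.

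**1. Growth needed to fail, read literally**

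- 4.9 to 5.0 mm: 0.1/4.9 = +2%, failure.
- 4.8 to 5.1 mm: 0.3/4.8 = +6%, failure.
- 4.5 to 5.0 mm: 0.5/4.5 = +11%, failure.
- Any baseline above 5/1.2 = 4.17 mm can fail with less than the 20% growth required in the measurable group.

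**2. The alternative reading.** Suppose appearance means only a lesion not seen before. Then a known 4 mm nodule growing to 15 mm never fails. Item (d) refers to new lesions where it means them; item (b) does not. Each reading misclassifies someone, and two assessors could score the same scans differently.

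**3. One truly unchanged nodule of 4.0 mm.** Reading error is assumed normal with SD s and independent between scans. The chance that one reading reaches 5 mm is p = 1 − Φ((5 − 4)/s). Over five scans it is 1 − (1 − p)^5.

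- s = 0.3: 0.2%
- s = 0.5: p = 0.0228, giving 1 − 0.9772^5 = 10.9%
- s = 0.75: p = 0.091, giving about 38%
- s = 1.0: p = 0.159, giving about 58%

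**4. A range of nodule sizes.** Simulation, 400,000 patients per setting. True size is constant and uniform on 2 to 5 mm, every baseline reading is below 5 mm, and there are five follow-up CTs. Failure is any reading of at least 5 mm while alive. Mortality is exponential with a 12-month median, from the 50% one-year figure in Section 14.0.

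| Assumed SD (mm) | One nodule, no deaths, 12 / 24 months | One nodule, plan's mortality, 24 months |
|---|---|---|
| 0.3 | 7% / 9% | 5.6% |
| 0.5 | 12% / 16% | 9.5% |
| 0.75 | 18% / 24% | 14.7% |
| 1.0 | 25% / 33–34% | 20.4% |

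The mortality column is nearer to what Section 14.0 would estimate, since death is a competing risk there. Three nodules at SD 0.5 give 40% at 24 months without deaths and 25% with them.

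**5. Dependence on size.** With true sizes uniform on 2 to 4 mm, SD 0.5, one nodule and no deaths, the 24-month figure falls from 16% to about 1%.

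**6. Expected number in the trial.** The subgroup size is not stated. As an illustration, five patients with three nodules each at SD 0.5, with the plan's mortality: 5 × 0.25 = about 1.2 false failures. With no such patients it is zero.

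**7. With a growth minimum of 3 mm.** Rule: at least 5 mm and at least 3 mm above the reference. One nodule, no deaths, 24 months:

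| Assumed SD (mm) | As written | Reference = pre-irradiation reading | Reference = smallest recorded reading |
|---|---|---|---|
| 0.5 | 16% | about 0% | about 0% |
| 0.75 | 24% | 0.7% | 1.6% |
| 1.0 | 33–34% | 4.9% | 9.9% |

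The smallest reading is itself selected for downward error, so using it as the reference lets noise accumulate.

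**The case against.** **The problem may be negligible in practice.** The documents give no reading error, no nodule-size distribution and no subgroup size. Patients with no residual nodules share the stratum and cannot be affected. This stands: the percentages show what the rule can do and do not forecast what will happen. A reader might infer one or two false failures as the expected outcome. That requires five multi-nodule patients, and the upper figure also requires ignoring the plan's mortality. Non-lung progression, another competing risk, and true lung progression, which would make the patient a failure anyway, are not modelled.

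**Reading noise is not peculiar to this group.** It is not. Under the same kind of assumptions, a single stable target lesion of 5 to 10 mm at SD 0.5 would be called progressive under item (d) in about 26% of cases by 24 months, more than the 16% here. A 4 mm nodule read as 5 mm is +25%, so it would meet a 20% rule as well; that example does not show a difference between the groups. The specific defect in item (b) is that it requires no change at all, which bites above 4.17 mm.

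**A 3 mm minimum brings its own inconsistency.** A 5.0 mm target lesion reaching 6.0 mm is progression under item (d), while a 4.0 mm nodule reaching 6.9 mm would remain stable. This also stands. The 3 mm value has no source in the documents and has to be set alongside item (d).

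**The endpoint is secondary.** Correct. A reader might infer that the trial's safety conclusion is compromised. The documents do not support that: the only decision rule, in Section 14.0, concerns 1-year toxicity and does not use CT response.

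**Conclusion.** The point holds as a definitional defect in a secondary endpoint with no hypothesis or threshold attached. Applied exactly, Section 12.2.1 scores a known nodule going from 4.8 to 5.1 mm as pulmonary failure, and the narrower reading of item (b) would let real growth go unscored.

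For one stable nodule uniform on 2 to 5 mm, false failure by 24 months is 9% to 34% without deaths and about 6% to 20% with the plan's mortality, over assumed SDs of 0.3 to 1.0 mm. The effect comes mainly from nodules between 4 and 5 mm. An upward bias in the lung-failure curve follows only if such patients enrol, and the documents do not say how many will. The rule should be corrected because it gives a wrong result when followed and the repair is cheap.

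**What to change.** Replace item (b) for patients without measurable disease at baseline with wording along these lines: PD is (i) a lung lesion of 5 mm or more that was not visible on the pre-irradiation CT, or (ii) a nodule visible but under 5 mm on that CT which later reaches 5 mm or more and has grown by at least a prespecified number of millimetres over its pre-irradiation diameter; otherwise SD.

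The sponsor sets the minimum; 3 mm is an example only. The reference should be the pre-irradiation reading, which performs better than the smallest recorded one. The number and diameters of sub-5 mm nodules should be recorded from the pre-irradiation CT.

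Two things should be settled in the same edit. The minimum should be chosen consistently with item (d), which has no absolute minimum and is also sensitive to reading error. The 10 mm upper bound on measurable lesions should be reconciled with the 2 cm eligibility limit, since eligible lesions of 10 to 20 mm are outside the definition as written.

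Cost: a short rewording and a few diameters from a scan already required; no added scans or patients. The downside is that true growth smaller than the minimum is called failure later, or not at all if the nodule stops growing.

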### **13.0 CRITERIA FOR REMOVAL FROM STUDY**

If at any time the patient desires to quit participation in the study or if the treating physician determines study participation is no longer appropriate, the patient will be removed from the study.

Toxicity will be evaluated in all patients enrolled who receive any whole-lung irradiation. Pulmonary progression free survival will only be evaluated in patients who complete all radiation treatments and have at least 1 follow-up chest CT.

### **14.0 BIOSTATISTICS**

The primary objective of this protocol is to assess the safety of whole lung IMRT following standard treatment in patients with synovial sarcoma and lung metastases. To this end we will enroll 15 eligible patients which will take about 6 years. Due to this long enrollment time the safety endpoint

will include both acute (<=3 months from the end of WLI) and late toxicities (>3 months from the end of WLI). Namely, we will evaluate the rate of any grade 3 toxicities (including pneumonitis, esophagitis, pericarditis and cardiac dysfunction) by using Kaplan-Meier estimation. If a patient withdraws from the protocol (expected to be 10% within 1 year), or dies without any grade 3 toxicities (expected to be 50% at 1 year) he/she will be regarded as a censoring at such time points. We will not use a competing risks analysis because it is expected that the withdrawal and death are independent from toxicities, and the actuarial estimate is believed to be more illustrative of the toxicity profile than the cumulative incidence rate by regarding death as a competing risk. For the decision rule we will look at the 1-year toxicity rate. If, the higher bound of the 85%, 1-sided confidence interval of the 1-year toxicity rate based on the (one minus) Kaplan-Meier estimate is lower than 0.25 than we will declare the whole lung IMRT procedure safe. This unusually high type 1 error rate, 15%, is used due to the rareness of such patients and the high progression/mortality rate without WLI. To roughly assess the power of the study with 15 patients, we simulated 10,000 datasets based on the above assumptions and examine the 1-year toxicity rate by Kaplan-Meier method. The following table shows probabilities of claiming whole lung IMRT safety under various values of the true 1-year toxicity rate.

True 1-year toxicity rate	0.05	0.10	0.15	0.20	0.25	0.30	0.35
Probability of claiming whole lung IMRT safe	0.894	0.712	0.536	0.364	0.243	0.154	0.094

As mentioned in Section 11.0, this study is also subject to early stopping if any radiation-related acute toxicities of grade 4 or higher are observed among the patients. If one of these events is observed in one patient, then the protocol will be closed to further accrual until reviewed by the principal investigator in conjunction with the investigators of the study.

Rates of pulmonary failure-free survival will be assessed by cumulative incidence functions. To this end pulmonary failure is the event of interest and other progressions and death are considered as the competing risks. Overall survival rates will be estimated by the Kaplan-Meier method.

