## 2.1 OBJECTIVES AND SCIENTIFIC AIMS

Primary objective

- To assess the overall toxicity rate at 1 year after whole lung IMRT in this patient population

Secondary objectives

- To determine rates of pulmonary failure-free survival after completion of whole lung IMRT.
- To determine rates of overall survival (OS) after completion of whole lung IMRT.

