### **10.1 Evaluations During Treatment**

All patients will undergo a routine status check visit approximately weekly during treatment. The maximum RT related toxicities graded by CTCAE version 4.0 will be submitted to the Research Study Assistant at the completion of WLI.

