## **12.0 CRITERIA FOR THERAPEUTIC RESPONSE/OUTCOME ASSESSMENT**

### **12.1 Assessment of Primary Objectives**

12.1.1 Assessment of the overall toxicity rate will occur at the pre-specified follow-up time-points using the CTCAE version 4.0 grading system. The radiation oncologist will score toxicity at each visit. Any toxicity recorded within three months of completion of radiation will be considered acute. Any toxicity after three months from completion of radiation will be considered late toxicity.

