## **16.1 DATA MANAGEMENT ISSUES**

A Research Study Assistant (RSA) will be assigned to the study. The responsibilities of the RSA include project compliance, data collection, abstraction and entry, data reporting, regulatory monitoring, problem resolution and prioritization, and coordinating the activities of the protocol study team.

The data collected from this study will be entered into a secure Clinical Research Database (CRDB). Source documentation will be available to support the computerized patient record.

Data collection will principally assess:

- Adherence to informed consent procedures. The informed consent must contain a full explanation of the possible advantages, benefits, risks, alternative treatment options, and availability of treatment in the case of injury, in accordance with Federal Regulations as detailed in 21CFR50. The investigator is responsible for obtaining written informed consent from potential patients. A copy of the signed document will be given to the patient, and the original will be retained by the investigator with his/her copy of the record forms.
- Adherence to eligibility criteria. The study RSA will ensure that documentation exists for all eligibility criteria and that the checklist is complete and signed by the consenting professional, prior to initiation of treatment. All supporting source documentation must be maintained in the patient's research file.
- Safety Evaluation: Radiation related toxicities will be recorded as they occur, and graded according to the CTCAE Version 4.0. Toxicities that cannot be graded using the CTCAE will be graded as grade 1 (mildly symptomatic), grade 2 (moderately symptomatic but not interfering significantly with function), grade 3 (causing significant interference with function), or grade 4 (life-threatening). All SAEs will be recorded, whether or not related to study treatment.
- The occurrence of unacceptable toxicity indicating the need for cessation of treatment will require mandatory reporting to the IRB. In this circumstance, the IRB will be consulted before a patient is removed from therapy. If the physician feels it is in the best interests of the patient to stop treatment, the IRB will be consulted.
- We expect to enroll 15 patients in 6 years. Since we are assessing two-year follow-up, we estimate that it will take 6 years to complete the study.

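### The primary endpoint has no consistent attribution rule, and with 15 patients one unrelated grade 3 event can reverse the 0.25 verdict

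*Combined protocol and SAP*

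**What the plan says.** **Endpoint text.** The primary objective in Section 2.1 is "To assess the overall toxicity rate at 1 year after whole lung IMRT in this patient population". Section 12.1.1 also speaks of an overall rate and adds: "The radiation oncologist will score toxicity at each visit". Section 14 turns this into the analysed event: "we will evaluate the rate of any grade 3 toxicities (including pneumonitis, esophagitis, pericarditis and cardiac dysfunction"). None of the three requires attribution to WLI. Section 14 censors patients who withdraw, or who die without a grade 3 toxicity. It does not mention progression or the start of new systemic therapy.

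**Collection text.** Section 16.1 (Data Management Issues) says "Radiation related toxicities will be recorded as they occur, and graded according to the CTCAE Version 4.0". For the treatment period, Section 10.1 says "The maximum RT related toxicities graded by CTCAE version 4.0 will be submitted to the Research Study Assistant at the completion of WLI". The same part of Section 16.1 also says "All SAEs will be recorded, whether or not related to study treatment", and the SAE report in Section 17.2 has a field for relationship to treatment.

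**Decision rule.** WLI is declared safe if the one-sided 85% upper bound of the 1-year rate (one minus Kaplan-Meier) is below 0.25.

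**The concern.** A rate of any grade 3 toxicity and a rate of radiation-related grade 3 toxicity are different endpoints, and the plan uses wording for both. Elsewhere it states attribution explicitly: the early-stopping paragraph of Section 14 refers to radiation-related events, and the suspension rule in Section 11 to WLI-related ones. Its absence from the endpoint sentence therefore cannot be put down to house style.

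The data would be a mixture. An unrelated grade 3 event that puts the patient in hospital is an SAE and will be recorded. One that is not serious may not be. Without a counting rule, the database cleanly supports neither an any-cause rate nor, until someone decides what to exclude, a related rate.

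This matters in a population where the plan itself expects 50% of patients to die within 1 year without a grade 3 toxicity. With 15 patients and a fixed threshold, the classification of one or two events can settle the conclusion. If that is decided after the events are known, the choice of definition can become the choice of verdict.

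**Working it through.** **Inputs from Section 14.** n = 15; death without grade 3 toxicity 50% at 1 year and withdrawal 10% within 1 year, both censored; one-sided 85% bound, z = 1.036; threshold 0.25. Not stated, so assumed: independent exponential times, Greenwood variance, and zero events counted as safe.

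**Step 1: reproduce the plan's table** (100,000 simulated trials per rate).

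| True 1-year rate | Plan | Log bound | Plain bound |
|---|---|---|---|
| 0.05 | 0.894 | 0.885 | 0.883 |
| 0.10 | 0.712 | 0.707 | 0.702 |
| 0.15 | 0.536 | 0.531 | 0.523 |
| 0.20 | 0.364 | 0.376 | 0.368 |
| 0.25 | 0.243 | 0.251 | 0.244 |
| 0.30 | 0.154 | 0.157 | 0.151 |
| 0.35 | 0.094 | 0.097 | 0.093 |

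The largest gap is 0.013. A log-log bound does not reproduce the table (0.778 at a rate of 0.05).

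**Step 2: one trial, one extra event.** With n_i at risk at each event, S = Π(1 − 1/n_i), V = Σ 1/[n_i(n_i − 1)], and the log upper bound is 1 − S·exp(−z√V).

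- One event, 14 at risk: S = 13/14 = 0.9286; V = 1/182 = 0.00549; bound = 1 − 0.9286 × exp(−1.036 × 0.0741) = **0.140**, safe.
- Add one unrelated event, 10 at risk: S = 0.9286 × 0.9 = 0.8357; V = 0.00549 + 1/90 = 0.01661; bound = 1 − 0.8357 × exp(−1.036 × 0.1289) = **0.269**, not safe (plain bound 0.276).
- The same extra event with 12 at risk: 0.244 (log) or 0.250 (plain), on the line.

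This step needs no assumed rate of unrelated events.

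**Step 3: operating characteristics over a range.** The documents give no rate of unrelated grade 3 events. Let q be an assumed 1-year rate, independent of the WLI-related rate p. If every cause counts, the total rate is 1 − (1 − p)(1 − q). Log bound, 60,000 trials per cell:

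| q (assumed) | Total, p = 0.05 | P(safe), p = 0.05 | Total, p = 0.10 | P(safe), p = 0.10 |
|---|---|---|---|---|
| 0 | 0.050 | 0.885 | 0.100 | 0.709 |
| 0.05 | 0.098 | 0.718 | 0.145 | 0.548 |
| 0.10 | 0.145 | 0.550 | 0.190 | 0.404 |
| 0.20 | 0.240 | 0.273 | 0.280 | 0.192 |
| 0.30 | 0.335 | 0.114 | 0.370 | 0.076 |

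The plan's own table gives a rough check. Totals of 0.098, 0.145 and 0.240 lie close to its columns for 0.10, 0.15 and 0.25, which read 0.712, 0.536 and 0.243.

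**The case against.** The strongest reply is that the plan means radiation-related toxicity throughout, and that *any* means any type. Several texts support this:

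- The four toxicities named in Section 14 all appear in Section 11 among the adverse events of WLI.
- Section 4.2 speaks of severe toxicity caused by radiation.
- Section 14 expects half the patients to die without a grade 3 toxicity and treats death as independent of toxicity. Both fit poorly with counting symptoms of fatal progression as toxicity.
- Lung progression has its own secondary endpoint.

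This reading is plausible, but Section 14 has no attribution wording and no other section settles the matter. It is also a reason to write the rule down.

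A reader might infer that the trial collects only radiation-related toxicity, so that unrelated events are never recorded and an any-cause rate is out of reach. The documents do not support that. All SAEs are recorded, their relationship to treatment is reported, and Section 12.1.1 scores toxicity at every visit without a filter. Section 10.1 covers only a course of about two weeks. The gap is narrower: non-serious grade 3 events judged unrelated, and the absence of a counting rule for serious ones.

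It is also fair to say that the size of the effect has no source in the documents. They describe no systemic therapy after WLI, and patients enter after completing planned therapy. Step 3 is therefore a range under an assumption; Step 2 is not affected.

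**Conclusion.** The concern stands as an inconsistency in the attribution rule for the primary endpoint, and it should be corrected. One unrelated event can move the upper bound from 0.140 to 0.269 and change the declared result. If unrelated events count, the probability of declaring safety at a WLI-related rate of 0.05 falls from 0.885 to between 0.718 and 0.114 for assumed unrelated rates of 0.05 to 0.30. Those figures rest on independence, exponential times and the plan's censoring rates.

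Two further inferences go too far. A reader might conclude that unrelated events would decide the verdict whatever WLI does. They would not: at an unrelated rate of 0.10 the probability of declaring safety is still 0.550 at a WLI-related rate of 0.05 and 0.404 at 0.10, so the WLI effect continues to matter. Nor is the probability table wrong. It reproduces for a single defined event rate; what is undefined is which event that rate describes.

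**What to change.** In Section 14, define the primary event as a CTCAE v4.0 toxicity of grade 3 or higher that is at least possibly related to WLI, attributed by the scoring radiation oncologist at each visit. The phrase *or higher* is needed because the present text says only grade 3. The possible-relationship standard is already used in the SAE definition of Section 11. State that events after progression or new systemic therapy count only if so attributed.

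Use the same wording in Sections 2.1, 10.1, 12.1.1 and 16.1 (Data Management Issues), and say that the table's true rate is the WLI-related rate.

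Record every grade 3 or higher event, serious or not, with an attribution field like the one on the SAE report. Report the any-cause 1-year rate as a sensitivity analysis, because attribution is made unblinded in a single-arm study. Settle the definition before toxicity data are reviewed.

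The cost is a wording change, one field on the toxicity form, and a little more data entry for 15 patients.

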#### **Definition of a Serious Adverse Events (SAE):**

- A Serious Adverse Event is an adverse experience that:
  - Is fatal or life-threatening
  - Is disabling
  - Results in hospitalization or prolongation of hospitalization
  - Results in a congenital anomaly or occurrence of malignancy
  - Any adverse event that is possibly related to WLI that is grade 3 or higher will be considered an adverse event.

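### As written, Section 14 counts only grade 3 toxicity: a first grade 4 event, or a WLI-caused death with no earlier recorded grade 3, stays out of the 1-year safety estimate

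*Combined protocol and SAP*

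**What the plan says.** Section 14.0 of the combined protocol and SAP holds the only grade-specific definition of the primary event: "we will evaluate the rate of any grade 3 toxicities", estimated by Kaplan-Meier with acute and late toxicity together. If a patient withdraws or "dies without any grade 3 toxicities (expected to be 50% at 1 year) he/she will be regarded as a censoring at such time points". The reason given for this, and for not using a competing-risks analysis, is that "it is expected that the withdrawal and death are independent from toxicities".

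The procedure is declared safe if the upper limit of a one-sided 85% confidence interval for the 1-year rate lies below 0.25. Fifteen patients are planned.

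Elsewhere the documents do say when higher grades are included. The definition of serious adverse events in Section 11.0 refers to "Any adverse event that is possibly related to WLI that is grade 3 or higher". The early-stopping paragraph at the end of Section 14.0 applies if "any radiation-related acute toxicities of grade 4 or higher are observed among the patients". The primary objective and Section 12.1.1 speak of an overall toxicity rate and give no grade threshold, so they do not settle the matter.

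**The concern.** The primary event and the censoring rule both turn on grade 3 alone. An analyst who follows the text exactly has no instruction to count two kinds of outcome:

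- a patient whose first severe toxicity is recorded at grade 4;
- a patient who dies because of WLI with no earlier recorded grade 3 toxicity. The censoring sentence covers this death, because it makes no exception by cause.

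The second is the firmer part. Censoring deaths is defended by independence between death and toxicity. A death caused by the toxicity is not independent of it.

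The safe or not-safe declaration rests on one bound in 15 patients. Whether the most serious outcomes enter that bound should be fixed in the text before the data are seen, not decided when such a case arises.

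**Working it through.** **Inputs (Section 14.0).** n = 15; one-sided 85% upper bound (z = 1.036); limit 0.25; 50% deaths and 10% withdrawals at 1 year, both censored.

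**1. The plan's table.** The type of interval is not named. The plain Greenwood bound was tried, with independent exponential times for toxicity, death and withdrawal and 100,000 datasets per rate. With no events the bound is 0.

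| True 1-year rate | 0.05 | 0.10 | 0.15 | 0.20 | 0.25 | 0.30 | 0.35 |
|---|---|---|---|---|---|---|---|
| Plan, P(declare safe) | 0.894 | 0.712 | 0.536 | 0.364 | 0.243 | 0.154 | 0.094 |
| Recomputed | 0.884 | 0.703 | 0.523 | 0.365 | 0.243 | 0.153 | 0.091 |

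The largest difference is 0.536 − 0.523 = 0.013. In a separate run of 20,000 datasets per rate, a log-transformed bound came within 0.010, while a log-log bound was off by up to 0.154. The table has one generic toxicity event, so it does not itself depend on which grades are meant.

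**2. Worked example, no other censoring.** Let S be the Kaplan-Meier estimate at 1 year and G = Σ d/[n(n − d)] over event times, with n at risk and d events. The plain bound is U = (1 − S) + z·S·√G.

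- *Two grade 3 events, third event ignored or censored after both.* S = 13/15 = 0.8667; G = 1/(15·14) + 1/(14·13) = 0.01026; U = 0.1333 + 1.036 × 0.0878 = **0.224**.
- *Two grade 3 events, WLI-caused death censored between them.* S = (14/15)(12/13) = 0.8615; G = 1/(15·14) + 1/(13·12) = 0.01117; U = 0.1385 + 1.036 × 0.0911 = **0.233**.
- *Two grade 3 events, WLI-caused death censored before both.* S = 12/14 = 0.8571; G = 1/(14·13) + 1/(13·12) = 0.01190; U = 0.1429 + 1.036 × 0.0935 = **0.240**.
- *Third event counted.* S = 12/15 = 0.8; G = 1/(15·14) + 1/(14·13) + 1/(13·12) = 0.01667; U = 0.2 + 1.036 × 0.1033 = **0.307**.

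The first three are below 0.25 (safe); the last is not.

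**3. Other forms of the bound.** The log-transformed bound gives the same verdicts: 0.220, 0.228 and 0.235 uncounted, 0.300 counted. The log-log bound is U = 1 − S^k with k = exp(z·√G/|ln S|).

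- One event: S = 0.9333, √G = 0.0690, |ln S| = 0.0690, k = 2.82, U = 0.177.
- Two events: S = 0.8667, √G = 0.1013, |ln S| = 0.1431, k = 2.08, U = 0.258.

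Under that form two events already fail, so the turning point is one counted event against two.

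**4. With the plan's own censoring.** In the step 1 simulation at a true rate of 0.25, the median plain bound is 0.181 with one counted event and 0.309 with two. One event still usually decides the matter, at a lower count.

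**5. Illustration only.** The documents do not say what share of first severe events would be grade 4 or 5. If 10, 20 or 30% of events went uncounted, P(declare safe) at a true rate of 0.25 would rise from 0.243 to 0.295, 0.355 or 0.421. At a true rate of 0.05, a 10% share moves it only from 0.884 to 0.898. These shares are assumptions, and the accrual hold is not modelled.

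**The case against.** **The intended meaning is plain.** The objective is an overall toxicity rate, and a grade 4 pneumonitis that closed accrual would hardly be left out of the toxicity count. This largely stands: the omission is probably a drafting slip. A reader might infer that the plan deliberately excludes grades 4 and 5, and nothing in the documents supports that. But no section states the intended reading for the endpoint, and Section 14.0 itself spells out higher grades for the accrual hold. Adding those words would also still leave the censoring sentence without an exception for a WLI-caused death.

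**Severe cases may already be counted at grade 3.** This stands in part. A reader might infer that every WLI-caused death is lost. That is not so: a death after a recorded grade 3 toxicity is already an event, at the earlier date. A reader might also infer, from Section 10.1 ("The maximum RT related toxicities graded by CTCAE version 4.0 will be submitted to the Research Study Assistant at the completion of WLI"), that earlier grade 3 episodes would not reach the analysis. That line describes one submission at the end of treatment. Toxicity is assessed weekly during WLI and scored at each visit, and Section 16.1 says "Radiation related toxicities will be recorded as they occur". The gap concerns first events only.

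**The accrual hold deals with such events.** It covers acute toxicity of grade 4 or higher and leads to a review. It does not add the event to the 1-year estimate, and late events fall outside it.

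**The size is hypothetical.** Fair. The worked example has no other censoring, although the plan expects a good deal. Section 11.0 lists pneumonitis and pulmonary fibrosis as rare, and Section 3.3.3 expects little clinically significant pulmonary toxicity at this dose. The documents do not show that such an event is likely, only that one would matter.

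**Two neighbouring points do not add to this one.** The fallback grading scale in Section 16.1 stops at grade 4. That matters only for a fatal, WLI-caused toxicity that CTCAE cannot grade and that had no earlier grade 3, which is remote. The varying terms for relatedness across sections are mostly near-synonyms and a separate matter.

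**Conclusion.** The point holds as a defect in the wording of the primary endpoint. Applied exactly, Section 14.0 leaves a first grade 4 event, or a WLI-caused death with no earlier recorded grade 3 toxicity, out of the estimate that decides safety. For that death, the plan's reason for censoring fails.

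In the worked example, one such event separates a bound of 0.224 to 0.240 (safe) from 0.307 (not safe). This assumes 15 patients, no other censoring and a plain Greenwood bound, which fits the plan's table to within 0.013. Under other forms of the bound, or heavier censoring, the count at which the conclusion turns may differ, but one event can still turn it. How often this would happen cannot be derived from the documents. If no such event occurs, the result is unaffected.

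A reader might go further and infer that censoring deaths is wrong in general, or that the sample size or table is invalid. Neither follows. Censoring deaths from disease or other causes is a stated, reasoned choice, and the table reproduces.

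The change should be made. Confidence is medium, because the literal reading is probably not the intended one.

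**What to change.** In Section 14.0:

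- define the primary event as the first CTCAE toxicity of grade 3 or higher (grades 3 to 5);
- count a death attributed to WLI as an event on its date, if no earlier event has been recorded;
- keep censoring deaths from disease or other causes.

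The 15 patients, the 0.25 limit and the table stay as they are, with the table's rate read as grade 3 or higher. A sensitivity analysis counting deaths of unknown cause as events is optional.

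The cost is a few sentences and an attribution for each death. SAE reports under Section 17.2 already record relationship to treatment. Deaths learned only from chart review or the social security database may need it added. If such events occur, the estimated rate will be higher and a declaration of safety less likely.
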